#### 8.2.4 Safety Analysis

Adverse event data will be summarized by treatment arm to capture the proportion of participants reporting at least one episode of a specific adverse event (incidence table), incidence of adverse events causing withdrawal, and incidence of serious adverse events. The total number of episodes for each event reported (frequency table), and the severity and attribution to treatment arm of each episode reported within body system (severity and attribution table), will also be displayed by treatment arm. Listings of adverse events by participants and event will also be provided. Comparisons of incidence of each adverse event between treatment and placebo will be performed using the two-group chi-square test, or Fisher's exact test when the assumptions for the chi-square test are not tenable. A two-sided statistical test with a significance level of 0.05 will be used for these analyses. In addition, 95% confidence intervals will be computed for differences in proportions of adverse events between study arms.

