#### 1.0 INTRODUCTION

#### 1.1 Study Rationale

The long-term efficacy and side effects of over-the-counter phytotherapies for men with lower urinary tract symptoms attributable to BPH are unknown, despite wide use of these agents by older men for maintaining "prostatic health." The overall goal of this study is to compare the efficacy of a widely available phytotherapy, extract of Serenoa Repens, against placebo in terms of impact on lower urinary tract symptoms. The phytotherapy selected for study has demonstrated short-term efficacy at relieving lower urinary tract symptoms with minimal side effects in a number of clinical trials. However, a recent NIDDK/NCCAM supported trial of Serenoa Repens at the 320 mg daily dose versus placebo did not demonstrate efficacy in terms of symptom reduction over 12 months of follow-up. As a result, this study is being conducted to compare higher-than-standard (double and triple) doses of this agent to determine its short-term effect on lower urinary tract symptoms and other parameters of BPH disease severity, and whether there is sufficient short-term efficacy and tolerability to merit testing for long-term efficacy in a long-term trial focused on the prevention of BPH progression. Because the study arm will use doses of this agent higher than generally used, participants will be monitored closely for toxicity/tolerability and have their doses slowly increased at 24-week intervals.

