#### 2.0 OBJECTIVES

#### 2.1 Primary objective

The primary objective of CAMUS is to determine if Serenoa Repens reduces the AUA symptom score compared to placebo over 72 weeks of treatment and is well tolerated.

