#### 4.3 Evaluations during Treatment and Follow-Up

- 4.3.1 Focused physical examination (including height and weight) and digital rectal examination at the 72 week visit.
- 4.3.2 Medical follow-up to include new diagnoses, treatments, hospitalizations, life events at the 4, 12, 24, 28, 36, 48, 52, 60 and 72 week visits.
- 4.3.3 Hematology: CBC and PT at the 12, 24, 36, 48, 60 and 72 week visits.
- 4.3.4 Serum chemistries: serum creatinine sodium, potassium, chloride, bicarbonate, glucose, ALT (SGPT), AST (SGOT) and GGT at the 12, 24, 36, 48, 60 and 72 week visits.
- 4.3.5 Urinalysis, including dipstick at the 72-week visit. If dipstick is positive (greater than 0) for blood or leukocyte esterase, then a specimen will be sent for microscopic analysis.
- 4.3.6 PSA at the 24, 48, and 72 week visits. The PSA measurements will be determined by a central laboratory. Please refer to the Manual of Operations for specimen collection and shipping instructions.
- 4.3.7 Vital signs at the 4, 12, 24, 28, 36, 48, 52, 60 and 72 week visits. (Visits 4, 28 and 52 can be optional phone interviews. A blood pressure monitor will be provided to participants to record blood pressure at home. The participant must agree to give 2 sitting readings to the study personnel.)
- 4.3.8 Uroflow measurement to include: voiding time, flow time, time to maximum flow, peak flow rate, mean flow rate, voided volume and post void residual at the 12, 24, 36, 48, 60 and 72 week visits.

- 4.3.9 Bladder Function, IPSS (AUA Symptom Score plus IPSS Quality of Life questions), and BPH Impact Index questionnaires, at the 12, 24, 36, 48, 60 and 72 week visits.
- 4.3.10 Erectile Function, Ejaculatory Function, NIH-CPSI, Jenkins Sleep Dysfunction Scale and Subjective Global Assessment, and participants' perception about whether they are on active therapy or placebo at the 24, 48, and 72 week visits.
- 4.3.11 Treatment compliance by pill count and provision of assigned study medication at the 12, 24, 36, 48, 60, and 72 week visits.
- 4.3.12 Adverse event assessment at the 4, 12, 24, 28, 36, 48, 52, 60, and 72 week visits.
- 4.3.13 Assessment of all medications, including over-the-counter medications, at the 4, 12, 24, 28, 36, 48, 52, 60 and 72 week visits, or when and adverse event occurs. (Visits 4, 28, and 52 can be omitted if optional phone interview chosen.)
- 4.3.14 Serum for banking at SV1.0 and 72 week visit.

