5) NOTE: If, after withdrawing the study medication, the participant's symptoms/abnormalities do not diminish, the investigator may wish to discuss re-challenge with the participant (since the symptoms may have been due to some cause other than the study medication). Careful monitoring of the participant should be observed during this re-challenge period. When assessing the potential causal relationship between the symptom/abnormality and the study medication, remember that the phytotherapy contains many fat-soluble constituents, so that the participant may have detectable tissue levels for several weeks after the medication is discontinued.

If subjects do not redevelop the side effect on re-challenge, they can remain on the final dose for that phase of the study until they have completed 24 total weeks of therapy at that dose, and then be escalated as called for in the protocol, unless they are already at triple dose, in which case they will be at the end of the study.

If on re-challenge, a participant once again develops the same side effect at a higher dose of study medication, but has tolerated a lower dose, he can be dropped back to the lower, tolerable dose for the rest of the study.

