Complete blood counts and serum chemistry measurements will be categorized by severity grade from the NCI Common Toxicity Criteria. For each participant and each time period on a dose level (1-24 weeks = level 1, 25-48 weeks = level 2, 49-72 weeks = level 3), the most severe grade of a laboratory level will be taken. For each dose level and laboratory measure, the proportions of participants who have abnormalities of severity grade 3 or greater will be compared between the phytotherapy and placebo arms using Fisher's exact test. A two-sided 0.05 significance level will be used for these comparisons.

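### Clinical adverse events are tabulated and compared by arm only, so the planned tables cannot show whether an excess arises at 320 mg or only at 640 or 960 mg

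*Combined protocol and SAP*

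**What the plan says.** Section 8.2.4 of the combined protocol and SAP sets out the clinical adverse event outputs. "Adverse event data will be summarized by treatment arm to capture the proportion of participants reporting at least one episode of a specific adverse event"; events causing withdrawal and serious events are handled in the same way. "The total number of episodes for each event reported (frequency table") and the severity and attribution table are also by arm. For testing, "Comparisons of incidence of each adverse event between treatment and placebo will be performed using the two-group chi-square test", or Fisher's exact test where chi-square is unsuitable, two-sided at 0.05, with 95% confidence intervals for differences in proportions. No dose level or time period is named. Listings by participant and event are planned, but their contents are not given.

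Section 8.2.3 treats laboratory data differently. It takes the worst grade within weeks 1-24, 25-48 and 49-72 and labels these dose levels 1 to 3. Then: "For each dose level and laboratory measure, the proportions of participants who have abnormalities of severity grade 3 or greater will be compared" between arms. The same section compares erectile and ejaculatory function, incontinence and sleep between arms at 24, 48 and 72 weeks, and gives the 24-week dose steps as the reason.

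Section 6.2 tabulates adverse events for the DSMB by arm and grade. Section 8.5 lets the DSMB set the content of its own safety reports.

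**The concern.** Section 1.1 says the trial was set up because an earlier trial at 320 mg daily showed no symptom benefit. It is to study double and triple doses and to judge "whether there is sufficient short-term efficacy and tolerability to merit testing for long-term efficacy" in a further trial. Section 2.1 puts tolerability in the primary objective: the extract is to be shown to reduce symptoms "compared to placebo over 72 weeks of treatment and is well tolerated". Section 1.2 reports no toxicity at 320 mg daily in the earlier trial, although with a different extract. Clinical tolerability at 640 and 960 mg is therefore the newer question.

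Anyone choosing a dose for a follow-on trial would want to know whether an excess was already present at the standard dose or appeared only after escalation. The planned tables cannot say. A period split chosen after unblinding would be open to the charge that it was picked to suit the data.

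**Working it through.** **The plan's own safety figure.** Section 8.1 gives 80% power for a laboratory-detected severe event at 2.5% on placebo against 10% on active, 157 per arm, one-sided 0.05. The continuity-corrected two-proportion formula needs 154 per arm for 80% and gives about 81% at 157, so the figure reproduces. It concerns laboratory events and sets no rate for clinical adverse events.

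**Inputs.** 157 men per arm (Section 8.1) and three 24-week blocks (Section 1.3). The documents give no rates for clinical adverse events, so every rate below is assumed. Blocks are independent, with at most one episode per man per block. Placebo: 2.5% per block. Pattern A: active 10% at 960 mg only, 2.5% otherwise. Pattern B: active 5% at every dose.

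**Incidence table** (at least one episode in 72 weeks):
- Placebo: 1 − 0.975³ = 7.3%; × 157 = 11.5 men.
- A: 1 − 0.975² × 0.90 = 14.4%; 22.7 men. The product is the same whichever block carries the 10%, so an excess at 320 mg only gives an identical table.
- B: 1 − 0.95³ = 14.3%; 22.4 men.

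Arm difference with Newcombe 95% interval: A 7.1 points (0.2 to 14.2); B 6.9 points (0.0 to 14.0).

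**Frequency table** (expected episodes):
- Placebo: 157 × 3 × 0.025 = 11.8.
- A: 157 × (0.025 + 0.025 + 0.10) = 23.6.
- B: 157 × 3 × 0.05 = 23.6.

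**What a period table would show** (expected men with an event, 157 × block rate):

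| | Weeks 1-24 | 25-48 | 49-72 |
|---|---|---|---|
| Placebo | 3.9 | 3.9 | 3.9 |
| Active, A | 3.9 | 3.9 | 15.7 |
| Active, B | 7.9 | 7.9 | 7.9 |

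The weeks 49-72 difference is 7.5 points (2.1 to 13.4) in A and 2.5 points (−2.0 to 7.4) in B. These intervals overlap, so the table describes a pattern and does not prove one.

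**Range.** Keep the fourfold and twofold patterns and set the block background to 1%, 5% or 10%. The 72-week incidence, A against B, is then 5.9% vs 5.9%, 27.8% vs 27.1% and 51.4% vs 48.8%, with expected episodes equal in each case. At the 2.5% background, if the same men tend to be affected (latent correlation 0.3, 0.5, 0.8), it is 13.5% vs 13.0%, 12.6% vs 11.8% and 10.8% vs 9.3%.

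**Power of the two-sided chi-square test at 0.05**, by exact binomial enumeration:

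| | Over 72 weeks | Within one period |
|---|---|---|
| A (weeks 49-72) | 54% | 81% |
| B | 52% | 20% |

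Neither test is better in both cases.

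**Chance patterns.** With three independent period counts, each binomial with 157 men and a 5% rate, the highest count is at least twice the lowest in about 42% of simulated trials.

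**The case against.** The strongest reply is that the plan answers the question it asks. In a forced-escalation design the randomized contrast is regimen against placebo over 72 weeks, and Section 2.1 words the objective that way. This stands. A reader might infer that the tolerability part of the primary objective goes unanswered, but it is answered for the regimen as a whole.

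A reader might also infer that the plan has no safety analysis by dose. Section 8.2.3 rules that out, with its laboratory comparison at each dose level and its patient-reported domains at 24, 48 and 72 weeks. Those analyses narrow the gap to clinical adverse events but do not replace a table of them.

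Nor is information lost. Section 8.2.4 states no time window, so whole-trial tables are the natural reading of silence and not an express rule. The listings may allow dose at onset to be reconstructed. But their contents are unspecified, and a listing is not a comparison between arms. The DSMB may request period reports, but that serves monitoring and adds nothing to the final analysis.

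Patterns A and B were chosen to have equal expected episodes. They show that the ambiguity is possible, not that it is likely. The point that moving a single-block excess to another dose leaves the incidence and frequency tables unchanged does not depend on that choice.

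Finally, a period split does not isolate dose. Period is confounded with time and cumulative exposure, and Section 5.2 notes that tissue levels may persist for weeks. Concurrent placebo men on matching capsule counts still give each period a control, and Section 8.2.3 accepts the same limitation for laboratory data.

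**Conclusion.** The point holds as a limited reporting gap. Clinical adverse events, including grade 3 or higher, serious and withdrawal-causing events, have no planned table by dose period. In the assumed example, the planned tables give 14.4% and 14.3% incidence and 23.6 episodes each for two quite different safety messages. The size rests wholly on assumed rates, because the documents give none. The primary efficacy test and data collection are unaffected.

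Two stronger readings are not supported. One is that significance tests by period should replace the 72-week test: power favours the period test in pattern A (81% vs 54%) and the 72-week test in pattern B (52% vs 20%). The reason to keep a single test per event is multiplicity control, not power. The other is that a period table would establish a dose effect: confounding with time and the 42% frequency of chance patterns argue against that. The change should be made before unblinding, as description only.

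**What to change.** Add to Section 8.2.4:

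*Each adverse event, and grade 3 or higher, serious and withdrawal-causing events, will also be tabulated descriptively by arm within weeks 1-24, 25-48 and 49-72. A man counts in every period in which an episode starts. Two denominators are shown: all men in follow-up at the start of the period, and men still taking study capsules at that time. A 95% confidence interval for the arm difference is given per period. The 72-week comparison remains the only significance test. Listings show capsules per day at onset (0 to 3).*

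The second denominator is needed because Sections 5.2 and 5.8 keep men who stop drug in follow-up. Counted in the weeks 49-72 column, they dilute the 960 mg rate, and intolerant men are the likeliest to have stopped. It does not remove men on a reduced dose, since after a failed rechallenge a man who tolerated less "he can be dropped back to the lower, tolerable dose for the rest of the study". Capsules per day at onset identifies the events among these men, though not their share of the denominator.

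The cost is SAP wording and extra table columns. No visits are added: Section 4.3 already plans "Adverse event assessment at the 4, 12, 24, 28, 36, 48, 52, 60, and 72 week visits", which is three per dose period. The fields of the adverse event form are not shown in the documents. If onset date is not recorded, the recording visit can assign the period, because the week 24, 48 and 72 visits close the blocks.

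Downsides: later periods and the on-drug denominator are less protected by randomization, and many per-period intervals will produce some chance excesses.

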#### 8.2.5 Subgroup Analysis

It is anticipated that the primary and secondary outcomes will be evaluated for racial/ethnic groups. Differences between the phytotherapy and placebo arms will be examined separately for each racial/ethnic group.

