#### 2.3 Subgroups

The primary and secondary outcome measures may vary by subgroups. Subgroup analyses will be conducted based on the following baseline measurements:

- 1. AUA Symptom Index and BPH Impact Index
- 2. Peak uroflow
- 3. Post-void residual volume

- 4. Prostate Specific Antigen (PSA) level
- 5. NIH Chronic Prostatitis Symptom Index

For each variable #1 - #4, three ordered categories will be created based on textiles of the respective distributions, and the relationship of the ordered categories to the outcome variables would be examined. For #5, the NIH-CPSI, the score will be dichotomized into two ordered categories, the threshold considered to indicate significant symptoms of chronic prostatitis.

Subgroup analyses of primary and secondary endpoints will be performed for subgroups defined by ethnicity and racial category.

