#### 8.0 STATISTICAL CONSIDERATIONS

#### 8.1 Sample size estimation

The primary goal of this study is to determine the efficacy and safety profile of treatment with *Serenoa Repens* compared to placebo. The primary end point of the study is change in AUA symptom score from baseline to 72 weeks. The sample size estimate is based on the following assumptions: a difference in the change in the AUA symptom score from baseline to 72 weeks of 2 points between the placebo arm and the phytotherapy arm, a common standard deviation of the AUA symptom score of 6 points, a two-group t- test, a one-sided significance level of 0.05 and a statistical power of 90%. A one-sided statistical test will be used since an improvement in the AUA symptom score with therapy (i.e., efficacy of therapy) is of primary interest. To detect the hypothesized difference in the change in the AUA symptom score, a sample size of 157 participants per arm will be required. Therefore, a total of 314 participants will be required for the study. To allow for a 10% dropout rate over the course of the study, 350 participants will be recruited to the study.

To determine the power for evaluating safety by measuring hematology and serum chemistry levels, it is assumed that the underlying probability of a severe or life-threatening adverse event detected by laboratory results for placebo is < 2.5%. With 157 participants in each treatment arm, the power to detect a severe or life-threatening adverse event that occurs with frequency  $\ge 10\%$  in the phytotherapy arm at the one-sided 0.05 significance level is 80%.

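### No treatment-by-subgroup interaction is stated in sections 2.3 or 8.2.5, so the plan as written does not test whether the treatment effect differs between subgroups

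*Combined protocol and SAP*

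**What the plan says.** Subgroups appear in two places in the combined protocol and SAP.

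Section 2.3 gives the motive, which is that outcomes may differ by subgroup. It lists baseline AUA score and BPH Impact Index, peak uroflow, post-void residual, PSA and NIH-CPSI. All but NIH-CPSI are cut into three ordered categories, and the method is that "the relationship of the ordered categories to the outcome variables would be examined". NIH-CPSI is split in two with no analysis named. Race and ethnicity are added, also with no method.

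Section 8.2.5, the analysis section, deals only with race and ethnicity: "Differences between the phytotherapy and placebo arms will be examined separately for each racial/ethnic group". It neither lists nor refers back to the baseline variables of section 2.3.

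The primary and secondary analysis sections (8.2.2 and 8.2.3) contain no treatment-by-subgroup term. Their Hochberg adjustment covers comparisons between timepoints, not subgroups.

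**The concern.** A subgroup question in a two-arm trial is whether the difference between arms changes from one subgroup to another. Neither stated method makes that comparison.

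- Relating a baseline category to outcome, with no treatment term, shows whether the category is prognostic. Men with higher baseline scores may improve more in both arms, which says nothing about the product.
- Comparing arms in each racial or ethnic group gives one effect per group, but nothing in the plan then sets those effects against each other.

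The gap invites a familiar error: treating a significant result in one group and a non-significant one in another as evidence that the effect differs. Smaller groups have less power, so they are the ones most likely to be labelled non-responders when the effect is the same for everyone. Section 9.3 commits the trial to representative minority participation, so these results are likely to be read with interest.

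**Working it through.** **Inputs from section 8.1.** The outcome: "The primary end point of the study is change in AUA symptom score from baseline to 72 weeks". The design effect: "a difference in the change in the AUA symptom score from baseline to 72 weeks of 2 points". The spread: "a common standard deviation of the AUA symptom score of 6 points". The test is one-sided at 0.05 with 90% power, and "a sample size of 157 participants per arm will be required".

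**Assumptions.** The documents give no racial or ethnic shares. I use 15 and 25 men per arm as examples of small groups, and minority shares of 10%, 20% and 30% of 157 per arm.

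**Step 1: the plan's own figure.** n per arm = 2 × (1.645 + 1.282)² × 6² / 2² = 154.2, so 155; the noncentral-t calculation also gives 155. The stated 157 agrees closely and gives about 90.5% power. For dropout, 314 / 0.9 = 349, against 350 in the plan.

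**Step 2: power within a small group when the true effect is 2 points everywhere.** The noncentrality is 2 / (6 × √(2/n)), one-sided 0.05, noncentral t.

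- n = 15 per arm: noncentrality 0.913, power 0.225 (about 23%).
- n = 25 per arm: noncentrality 1.179, power 0.315 (about 31%).

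**Step 3: how often two separate tests would disagree under that uniform effect.** With group powers p₁ and p₂ (normal approximation, one-sided 0.05), P(disagree) = p₁(1 − p₂) + p₂(1 − p₁).

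| Minority share (assumed) | n per arm, minority / majority | p₁ | p₂ | P(disagree) |
|---|---|---|---|---|
| 10% | 15.7 / 141.3 | 0.239 | 0.876 | 0.70 |
| 20% | 31.4 / 125.6 | 0.373 | 0.841 | 0.59 |
| 30% | 47.1 / 109.9 | 0.489 | 0.796 | 0.51 |

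For 10%: 0.239 × 0.124 + 0.876 × 0.761 = 0.030 + 0.667 = 0.70.

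**Step 4: what an interaction test could detect.** For two groups, SE = 6 × √(2/n₁ + 2/n₂). Two-sided 0.05 power for a 2-point difference in effect is Φ(2/SE − 1.96). The difference detectable with 80% power is 2.80 × SE.

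| Split | SE (points) | Power for a 2-point difference | Detectable at 80% power |
|---|---|---|---|
| 50 / 50 | 1.35 | 31% | 3.8 points |
| 30 / 70 | 1.48 | 27% | 4.1 points |
| 20 / 80 | 1.69 | 22% | 4.7 points |
| 10 / 90 | 2.26 | 14% | 6.3 points |

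For a linear trend in effect across tertiles (about 52 men per arm in each), the effect in one tertile has variance 2 × 36 / 52.33 = 1.376, and the slope per step has SE √(1.376/2) = 0.83. If the top and bottom tertile effects differ by 2 points (slope 1), power is Φ(1/0.83 − 1.96) = 23%. The top-to-bottom difference detectable with 80% power is 2 × 2.80 × 0.83 = 4.6 points.

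**The case against.** The best defence is that the text is loose rather than wrong. Section 8.2.5 says effects will be examined; it names no test, level or decision rule, and no passage plans to infer a difference from a split in significance. Within-group estimates could be compared informally. Section 2.3 is vague enough that a trend in treatment effect across the ordered categories may have been meant. No objective in sections 2.1 and 2.2 rests on a subgroup, and the primary test and sample size are untouched. An interaction test would also usually miss a 2-point difference.

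Most of this stands, and it limits the point in three ways.

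- A reader might infer that the planned analyses are incapable of showing a difference in effect. The documents do not support that, because estimates by group could be set side by side. They support only that no such comparison is stated.
- A reader might count every tertile and category as a separate arm test and predict a crop of false positives. Separate arm comparisons are stated only for race and ethnicity. With five such groups (assumed), each tested at 0.05, the expected number is 5 × 0.05 = 0.25 per outcome when there is no effect, and even that presumes tests that the text does not name.
- A reader might want the AUA tertiles replaced by the randomisation bands of section 3.3 (8-15 and 16-24). That is a preference; nothing shows the tertiles to be wrong.

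The vagueness does not remove the need for a change. If an interaction was intended, it should be written down. Low power is no defence of separate comparisons; it is a reason to report the interaction with its uncertainty. The absence of the baseline variables from 8.2.5 is a cross-reference gap, since section 2.3 does define them.

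**Conclusion.** The point holds as a gap in specification. As written, the plan does not test whether the treatment effect differs between subgroups: one section describes an association with no treatment term, the other a set of separate arm comparisons, and no interaction is stated anywhere.

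The size depends on the design values of section 8.1, on a uniform true effect, on separate tests being run at one-sided 0.05, and on assumed group sizes. On that basis, small groups would miss a real 2-point effect about 69% to 77% of the time, and two-group comparisons would disagree in roughly half to seven-tenths of trials with no difference in effect. Larger subgroups would fare better.

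The change should be made, but the weight is moderate. These are supporting analyses, and the primary conclusion does not depend on them.

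**What to change.** Rewrite section 8.2.5 to cover every variable in section 2.3 as well as race and ethnicity.

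- **Model.** For the primary endpoint, fit change at 72 weeks on treatment, subgroup and their interaction. Use a linear trend across the prespecified tertiles, or the continuous baseline value, for the ordered variables. Use categorical terms for NIH-CPSI and for race and ethnicity.
- **Reporting.** Give the interaction estimate with its 95% confidence interval and p-value, beside within-group estimates with 95% confidence intervals.
- **Interpretation.** State that no subgroup difference will be inferred from significance within groups, and label the analyses exploratory.
- **Limits.** State the low interaction power (about 31% for a 2-point difference between equal halves, and 14% to 27% for minority shares of 10% to 30%), and that a non-significant interaction is not proof of a uniform effect.

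The cost is SAP wording only: no added participants, visits or data. The drawback is that the interaction results will often be inconclusive, and the text should say so in advance.
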